7.5 An Overdose for this Protocol

7.5.1 Definition and Assessment of an Overdose for this Protocol

For purposes of this trial, an overdose of pembrolizumab will be defined as any dose of 1,000 mg or greater (\geq 5 times the indicated dose).

No specific information is available on the treatment of overdose of pembrolizumab. Appropriate supportive treatment should be provided if clinically indicated. In the event of overdose, the subject should be observed closely for signs of toxicity. Appropriate supportive treatment should be provided if clinically indicated.

7.5.2 Reporting of an Overdose for This Protocol

If an adverse event(s) is associated with ("results from") the overdose of a Merck product, the adverse event(s) is reported as a serious adverse event, even if no other seriousness criteria are met.

If a dose of Merck's product meeting the protocol definition of overdose is taken without any associated clinical symptoms or abnormal laboratory results, the overdose is reported as a non-serious Event of Clinical Interest (ECI), using the terminology "accidental or intentional overdose without adverse effect."

All reports of overdose with and without an adverse event must be reported within 24 hours to the Sponsor-Investigator and within 2 working days hours to Merck Global Safety. (Attn: Worldwide Product Safety; [contact]).

7.6 Reporting of Pregnancy and Lactation to the Sponsor and to Merck

Although pregnancy and lactation are not considered adverse events, it is the responsibility of investigators or their designees to report any pregnancy or lactation in a subject (spontaneously reported to them) that occurs during the trial.

Pregnancies and lactations that occur after the consent form is signed but before treatment allocation/randomization must be reported by the investigator if they cause the subject to be excluded from the trial, or are the result of a protocol-specified intervention, including but not limited to washout or discontinuation of usual therapy, diet, placebo treatment or a procedure. Pregnancies and lactations that occur from the time of treatment allocation/randomization through 120 days following cessation of Sponsor's product, or 30 days following cessation of treatment if the subject initiates new anticancer therapy, whichever is earlier, must be reported by the investigator. All reported pregnancies must be followed to the completion/termination of the pregnancy. Pregnancy outcomes of spontaneous abortion, missed abortion, benign hydatidiform mole, blighted ovum, fetal death, intrauterine death, miscarriage and stillbirth must be reported as serious events (Important Medical Events). If the pregnancy continues to term, the outcome (health of infant) must also be reported.

Such events must be reported within 24 hours to the Sponsor-Investigator and within 2 working days to Merck Global Safety. (Attn: Worldwide Product Safety; [contact]).

7.7 Definition of Unanticipated Problems (UAP)

The Office of Human Research Protection (OHRP) considers unanticipated problems involving risks to participants or others to include, in general, any incident, experience, or outcome that meets **all** of the following criteria:

- Unexpected in terms of nature, severity, or frequency given (a) the research procedures that are described in the protocol-related documents, such as the IRB-approved research protocol and informed consent document; and (b) the characteristics of the participant population being studied;
- Related or possibly related to participation in the research ("possibly related" means there is a reasonable possibility that the incident, experience, or outcome may have been caused by the procedures involved in the research); and
- Suggests that the research places participants or others at a greater risk of harm (including physical, psychological, economic, or social harm) than was previously known or recognized.

This study will use the OHRP definition of UAP.

7.8 Evaluating Adverse Events

An investigator who is a qualified physician will evaluate all adverse events according to the NCI Common Terminology for Adverse Events (CTCAE), version 4.0. Any adverse event which changes CTCAE grade over the course of a given episode will have each change of grade recorded on the adverse event case report forms/worksheets.

All adverse events regardless of CTCAE grade must also be evaluated for seriousness.

7.9 Sponsor-Investigator Responsibility for Reporting Adverse Events

All Adverse Events will be reported to regulatory authorities, IRB/IECs and investigators, in accordance with all applicable global laws and regulations.

Table 11: Evaluating Adverse Events

An investigator who is a qualified physician, will evaluate all adverse events as to:

| V4.0 CTCAE Grading | CTCAE Grade 1 Mild; asymptomatic or mid symptoms; clinical or diagnostic observations only; intervention not indicated. | | |
|--|--|---|--|
| | Grade 2 Moderate; minimal, local or noninvasive intervention indicated; limiting age-appropriate instrumental ADL. | | |
| Grade 3 Severe or medically significant but not immediately l limiting self-care ADL. | | Severe or medically significant but not immediately life-threatening; hospitalization or prolongation or hospitalization indicated; disabling; limiting self-care ADL. | |
| | Grade 4 | Life threatening consequences; urgent intervention indicated. | |
| | Grade 5 | Death related to AE | |
| Seriousness | A serious adv | verse event is any adverse event occurring at any dose or during any use of Merck product that: | |
| | †Results in death; or | | |
| | †Is life threatening; or places the subject, in the view of the investigator, at immediate risk of death from the event as it occurred (Note: This does not include an adverse event that, had it occurred in a more severe form, might have caused death.); or | | |
| | †Results in a | persistent or significant disability/incapacity (substantial disruption of one's ability to conduct normal life functions); or | |
| | †Results in or prolongs an existing inpatient hospitalization (hospitalization is defined as an inpatient admission, regardless of hospitalization is a precautionary measure for continued observation. (Note: Hospitalization for an elective procedure to treat a pre-exist worsened is not a serious adverse event. A pre-existing condition is a clinical condition that is diagnosed prior to the use of a Merck produsubject's medical history.); or | | |
| | †Is a congenital anomaly/birth defect (in offspring of subject taking the product regardless of time to diagnosis);or | | |
| | Is a new cancer (that is not a condition of the study) (although not serious per ICH definition, is reportable to the Sponsor within 24 hours and to Merck within 2 working days to meet certain local requirements); or | | |
| | Is an overdo overdose that Merck within | se (whether accidental or intentional). Any adverse event associated with an overdose is considered a serious adverse event for collection purposes. An t is not associated with an adverse event is considered a non-serious event of clinical interest and must be reported within 24 hours to the Sponsor and to a 2 working days. | |

| | Other important based upon appr previously (design | nt medical events that may not result in death, not be life threatening, or not require hospitalization may be considered a serious adverse event when, ropriate medical judgment, the event may jeopardize the subject and may require medical or surgical intervention to prevent one of the outcomes listed gnated above by a [†]). |
|----------------------------------|---|---|
| Duration | Record the start | and stop dates of the adverse event. If less than 1 day, indicate the appropriate length of time and units |
| Action taken | Did the adverse | event cause Merck product to be discontinued? |
| Relationship to Merck Product | Did Merck product cause the adverse event? The determination of the likelihood that Merck product caused the adverse event will be provided by an investigator who is a qualified physician. The investigator's signed/dated initials on the source document or worksheet that supports the causality noted on the AE form, ensures that a medically qualified assessment of causality was done. This initialed document must be retained for the required regulatory time frame. The criteria below are intended as reference guidelines to assist the investigator in assessing the likelihood of a relationship between the test drug and the adverse event based upon the available information. The following components are to be used to assess the relationship between Merck product and the AE; the greater the correlation with the components and their respective elements (in number and/or intensity), the more likely Merck product caused the adverse event (AE): | |
| | Exposure | Is there evidence that the subject was actually exposed to Merck product such as: reliable history, acceptable compliance assessment (pill count, diary, etc.), expected pharmacologic effect, or measurement of drug/metabolite in bodily specimen? |
| | Time Course | Did the AE follow in a reasonable temporal sequence from administration of Merck product? Is the time of onset of the AE compatible with a drug-induced effect (applies to trials with investigational medicinal product)? |
| | Likely Cause | Is the AE not reasonably explained by another etiology such as underlying disease, other drug(s)/vaccine(s), or other host or environmental factors |

| Relationship | The following components are to be used to assess the relationship between the test drug and the AE: (continued) | |
|---|--|--|
| to Merck Product | Dechallenge | Was Merck product discontinued or dose/exposure/frequency reduced? |
| (continued) | | If yes, did the AE resolve or improve? |
| | | If yes, this is a positive dechallenge. If no, this is a negative dechallenge. |
| | | (Note: This criterion is not applicable if: (1) the AE resulted in death or permanent disability (2) the AE resolved/improved despite continuation of the Sponsor's product; or (3) the trial is a single-dose drug trial); or (4) Sponsor's product(s) is/are only used one time.) |
| | Rechallenge | Was the subject re-exposed to Merck product in this study? |
| | | If yes, did the AE recur or worsen? |
| | | If yes, this is a positive rechallenge. If no, this is a negative rechallenge. |
| | | (Note: This criterion is not applicable if: (1) the initial AE resulted in death or permanent disability, or (2) the trial is a single-dose drug trial); or (3) Sponsor's product(s) is/are used only one time). |
| | | NOTE: IF A RECHALLENGE IS PLANNED FOR AN ADVERSE EVENT WHICH WAS SERIOUS AND WHICH MAY HAVE BEEN CAUSED BY MERCK PRODUCT, OR IF REEXPOSURE TO MERCK PRODUCT POSES ADDITIONAL POTENTIAL SIGNIFICANT RISK TO THE SUBJECT, THEN THE RECHALLENGE MUST BE APPROVED IN ADVANCE BY THE SPONSOR AS PER DOSE MODIFICATION GUIDELINES IN THE PROTOCOL. |
| | Consistency with Trial | Is the clinical/pathological presentation of the AE consistent with previous knowledge regarding Merck product or drug class pharmacology or toxicology? |
| | l reatment Profile | The assessment of relationship will be reported on the case report forms /worksheets by an investigator who is a qualified physician according to his/her best clinical judgment, including consideration of the above elements. |
| | Use the following | g scale of criteria as guidance (not all criteria must be present to be indicative of Merck product relationship) |
| Yes, there is a reasonable possibility of Merck product relationship | | There is evidence of exposure to Merck product. The temporal sequence of the AE is more likely explained by Merck product than another cause. The AE onset relative to administration of Merck product is reasonable. |
| No, there is not a reasonable possibility of Merck product relationship | | Subject did not receive the Merck product OR temporal sequence of the AE onset relative to administration of Merck product is not reasonable OR is more likely explained by another cause than the Merck product.(also entered for a subject with overdose without an associated AE.) |

8.0 STATISTICAL ANALYSIS PLAN

8.1 Statistical Analysis Plan Summary

The final study analysis will be based on subject data collected through study discontinuation. Analyses will be based on the safety-evaluable population, defined as all subjects who receive any amount of study treatment. In general, data will be summarized as warranted, and listings will be provided in place of tables when sample sizes are small. Summaries will be presented by the assigned dose regimen and designated treatment arm.

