2.1.3 Dose Escalation Rules

Pembrolizumab will be administered at a fixed dose of 200 mg IV every 21 days on Day 1 of each cycle.

The starting dose of cabozantinib for subjects in the first cohort will be 40 mg PO once daily for 21 consecutive days of each cycle (Days 1–21). For the second cohort, the dose of cabozantinib will be 60 mg PO once daily. If the starting dose of 40mg is not tolerated (2 or more out of 6 subjects experiencing DLT), then a lower dose of 20 mg will be evaluated.

Once the DLT assessment period has passed, pembrolizumab and/or cabozantinib may be held or dose modified independent of the other agent for adverse events attributed to one but not both drugs. The Principal Investigator should be notified when this occurs.

In addition to any DLTs, other available relevant demographic, adverse event, laboratory, and dose administration data will be reviewed prior to all dose-escalation decisions.

Dose escalation will occur in accordance with the rules:

- A minimum of 3 subjects will be enrolled in each cohort.
- If none of the first 3 DLT-evaluable subjects experiences a DLT, enrollment of the next cohort may proceed.
- If 1 of the first 3 DLT-evaluable subjects experiences a DLT, the cohort will be expanded to a minimum of 6 subjects. If there are no further DLTs in the first 6 DLT-evaluable subjects, enrollment of the next cohort may proceed.
- If 2 or more of the first 6 DLT-evaluable subjects in a cohort experience a DLT, the MTD will have been exceeded and dose escalation will stop. The preceding cohort will also be expanded to a minimum of 6 subjects, unless 6 subjects have already been evaluated at that dose level.
- If the MTD is exceeded at any dose level, the highest dose at which fewer than 2 of 6 DLTevaluable subjects experience a DLT will be declared the MTD.
- If the MTD is not exceeded at any dose level, the highest dose administered in this study will be declared the maximum administered dose.
- Any dose level may be expanded in the absence of a DLT if warranted based on investigator evaluation of non-DLT adverse events, including events occurring after Cycle 1 and events observed in the expansion cohorts.
- To be considered evaluable for dose escalation, subjects must have received at least 1 dose of pembrolizumab and ≥75% of planned dosing of cabozantinib prior to completing the DLT assessment window of 21 days.

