2.1.6 Intra-Subject Dose Escalation

There will be no dose reduction or escalation of pembrolizumab, which is to be administered at a fixed dose of 200 mg IV every 21 days.

Intra-subject dose escalation of cabozantinib to a higher dose level will be allowed if all of the following conditions are met:

- One or fewer of the first 3 DLT-evaluable subjects, or fewer than 2 of the first 6 DLTevaluable subjects experience a DLT at the higher dose level cohort.
- The subject has completed at least 3 cycles at their originally assigned dose level.
- The subject has not experienced a DLT or an adverse event occurring outside the DLT window that would otherwise meet the definition of a DLT.
- The subject is clinically stable with no decrement in performance status.
- The Principal Investigator has approved the dose escalation.
- The overall benefit/risk balance favors continued treatment, in the opinion of the investigator.

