8.2.2 Analysis of Safety

Safety will be assessed through summaries of DLTs, adverse events, clinically significant changes in laboratory test results, clinically significant changes in vital signs and ECGs, and exposure to components of study treatment. All subjects who receive any amount of study treatment will be included in the safety analyses.

Adverse event data will be listed by dose cohort. Events occurring on or after treatment on Cycle 1, Day 1 will be summarized by AE term, NCI CTCAE v4.0 grade, and relationship to either pembrolizumab and/or cabozantinib.

Serious adverse events, including deaths, will be listed separately and summarized.

Adverse events leading to treatment discontinuation will be listed.

Adverse events meeting the criteria for DLT will be listed. Subjects who withdraw from the study prior to completing the DLT assessment window for reasons other than a DLT will be considered unevaluable for DLT assessments.

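### Adverse events are presented only by assigned dose although a subject's cabozantinib dose can change, so late toxicity is blurred between dose levels

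*Combined protocol and SAP*

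**What the plan says.** Section 8.1 sets the grouping for the final analysis: "Summaries will be presented by the assigned dose regimen and designated treatment arm". Section 8.2.2 follows it for safety: "Adverse event data will be listed by dose cohort", with summaries by term, grade and relationship to either drug. It also summarises "exposure to components of study treatment", but does not link exposure to the timing of events.

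The dose a subject takes need not stay at the assigned level:

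- **Upward.** Section 2.1.6: "Intra-subject dose escalation of cabozantinib to a higher dose level will be allowed", subject to conditions. One is that "The subject has completed at least 3 cycles at their originally assigned dose level". Another concerns DLTs at the higher level: "One or fewer of the first 3 DLT-evaluable subjects, or fewer than 2 of the first 6".
- **Downward.** Table 4 in 5.2.1.4 provides for cabozantinib reductions after toxicity.

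Late events have stated uses. Section 2.1.3 lets a dose level be expanded on the basis of non-DLT events, "including events occurring after Cycle 1 and events observed in the expansion cohorts". Section 2.1.5 lets the RP2D be amended as safety data accumulate in Phase II.

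No section attributes an event to the dose being taken when it began, cuts follow-up at a dose change, or shows post-escalation events apart.

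**The concern.** Assigned dose and dose taken diverge by design, and the safety tables follow only the first. An event at 60 mg in a subject who escalated from 40 mg appears in the 40 mg row and nowhere in the 60 mg row. An event at 40 mg in a subject reduced from 60 mg stays in the 60 mg row. Both displacements blur the contrast in late toxicity between the two levels.

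At stake is how far the post-Cycle 1 safety data can be read by dose, both in the final report and wherever summaries grouped this way inform the judgements in 2.1.3 and 2.1.5.

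**Working it through.** **1. The plan's own dose-finding figures.** Table 12 holds the only stated probabilities tied to judging the dose. They are exact binomial: (1−p)³ for no DLT in 3, and (1−p)⁶ + 6p(1−p)⁵ for fewer than two in 6. At p = 0.33 these give 0.67³ = 0.301 and 0.0905 + 0.2673 = 0.358, against the stated 0.30 and 0.36. Every other cell also reproduces to rounding. None of them depends on how adverse events are grouped.

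**2. Can an escalated dose enter the DLT counts?** Inputs: 21-day cycles (Section 6.0), a DLT window of Days 1–21 (2.1.1), and at least 3 cycles before escalation (2.1.6).

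- Earliest escalation: after 3 × 21 = 63 days.
- Gap from the close of the window: 63 − 21 = 42 days.

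No day of the DLT window is misattributed. Section 2.1.1 allows the window to be extended without giving a length; it would have to run past day 63 for this to change.

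**3. How much later treatment can be misattributed?** Input: the estimated average treatment of 8 months (Section 1.0). With 30.4375 days per month:

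- Total: 8 × 30.4375 = 243.5 days.
- At the higher dose, escalating at the first opportunity: 243.5 − 63 = 180.5 days.
- Share: 180.5 / 243.5 = 74%.

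Range: about 48% for an assumed 4 months, (121.75 − 63) / 121.75, and 91% for 35 cycles, 32/35. These are shares of time for one subject, not errors in a toxicity rate.

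**4. What this could do to a row of the table.** The documents give no late-event rates by dose, so the rates here are assumed. Suppose each escalated subject takes on the 60 mg rate in full. With m of 6 subjects escalating, the expected rate in the 40 mg row is [(6 − m) × rate at 40 mg + m × rate at 60 mg] / 6.

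| Assumed late-event rate, 40 mg / 60 mg | m = 0 | m = 1 | m = 3 | m = 6 |
|---|---|---|---|---|
| 10% / 30% | 10% | 13% | 20% | 30% |
| 20% / 40% | 20% | 23% | 30% | 40% |
| 20% / 50% | 20% | 25% | 35% | 50% |

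One escalator shifts the expected rate by 3 to 5 percentage points. If all six escalate, the expected rate in the 40 mg row equals the 60 mg rate. In observed data, one subject's event is worth 1/6 = 17 points in a cohort of 6 and 1/3 = 33 points in a cohort of 3.

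**5. Who can be affected?** If 60 mg clears, it becomes the RP2D and no higher level exists, so upward moves come essentially from the 40 mg cohort of 3 to 6 subjects. One route is wider. The two parts of the 2.1.6 condition are joined by *or*. Read literally, one DLT in the first 3 at 60 mg satisfies it even if two or more of 6 later have DLTs. The probability of exactly one DLT in the first 3 and at least one in the next 3 is 3p(1−p)² × [1 − (1−p)³]. For assumed 60 mg DLT rates of 0.20, 0.33, 0.40 and 0.50 it is 0.19, 0.31, 0.34 and 0.33. In that event 40 mg could be the RP2D while its row contains 60 mg exposure. Sections 2.1.3, 2.1.5 and 2.1.6 must be reconciled on this.

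**The case against.** The case for leaving the plan alone has several parts.

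- **The grouping rule belongs to the final analysis.** Section 8.1 says so, whereas the decisions in 2.1.3 and 2.1.5 are continuing reviews by investigators. Dose administration data are part of the review before escalation decisions, and 10.6.1 has toxicities and dose modifications discussed together. This stands: nothing shows that those reviews would rely on assigned-dose tables. The late-safety judgements are exposed only so far as they do.
- **The affected cohort is small.** Section 8.1 substitutes listings for tables when numbers are small, and treatment administration is reported under 8.2.1. A careful reader could recover the dose at onset. This limits the harm, but the plan does not call for that link to be shown.
- **Assigned-dose tables answer a legitimate question**, namely toxicity by starting dose. This stands, and is a reason to keep them.
- **Dose at onset has its own biases.** Escalators are selected: they must have had no DLT-type event and be clinically stable. Section 5.2.1.3 notes that immune events may appear months after the last dose, so the dose at onset need not be the causal one. This also stands, and makes the added tables descriptive.

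A reader might go further and infer that 60 mg will look safer than it is. The documents do not support that. Escalators assigned to 40 mg are absent from both numerator and denominator of the 60 mg row, so their events do not lower its incidence; events after a reduction remain in that row and can only add to it. What follows is a blurred contrast.

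**Conclusion.** The gap is real and worth closing, but its reach is limited. Adverse events are presented only by assigned dose or dose cohort, dose changes are allowed in both directions, and no rule separates events before and after a change. The late-toxicity comparison between dose levels is therefore blurred.

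The size is up to 74% of an average 8-month treatment for a subject who escalates as early as allowed, mainly in a cohort of 3 to 6. The effect on rates depends on how many subjects escalate and on late-event rates that the documents do not give. For reductions, the only frequency available is the 60% (197 of 331) that 4.2.2.2 cites from the phase III study of cabozantinib against everolimus. That is context, not a forecast for this combination.

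It is tempting to conclude that the MTD and RP2D objective is compromised. It is not: the MTD and the initial RP2D rest on Cycle 1 DLTs, which are counted before any escalation can occur. That holds unless the DLT window is extended beyond day 63.

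**What to change.** In 8.1 and 8.2.2, keep the assigned-dose summaries and the Cycle 1 DLT tables, and add:

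1. Adverse event tables by the cabozantinib dose being taken at onset, with exposure time at each dose as the denominator.
2. A display or flag of each escalated subject's events before and after the change.
3. A derivation rule for events that begin during a dose interruption, and for events that worsen after a dose change. Section 7.8 already has each change of grade recorded.
4. A sentence saying that these tables are descriptive, because escalators are selected for tolerance and immune events may be delayed.

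Separately, reconcile 2.1.3, 2.1.5 and 2.1.6 on whether escalation remains open once the higher level has two or more DLTs in 6. This review takes no position on which clinical rule should apply.

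The cost is SAP wording, one extra derivation and one further set of tables. Event start and stop dates (Table 11) and the medication diary (5.2.2) are already collected. Sample size, type I error, power and Table 12 do not change.
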